### **The total number of participants and how they will be recruited:**

The experiment will be carried out in the Department of Oral and Maxillofacial Surgery at Sheba Tel Hashomer Medical Center.

Up to 10 participants are needed to demonstrate that the LOPO device effectively positions the working cannula regardless of anatomical variation among individuals.

Candidates for the procedure are patients diagnosed in our department with closed lock, Wilkes stage 3, based on anamnesis, clinical examination, and imaging, for whom TMJ arthroscopy is the accepted treatment. These patients will receive the standard preoperative explanation about the procedure, including its course, expected results, potential risks, the necessity for post-operative physical therapy, and the requirement to avoid hard foods for a month after arthroscopy. Additionally, they will be informed about our intention to use the LOPO device and asked for their consent. Patients who consent to using the LOPO during surgery will receive a letter for their family doctor detailing the procedure and the device.

The patients will be treated using the standard arthroscopic tool set available at Sheba, along with the LOPO device we developed.

Participants will not receive any financial compensation or other benefits. It will be explained that their participation contributes to scientific and medical advancements. Successful performance of the device in real patients will significantly advance the field of TMJ arthroscopy.

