As previously mentioned, the initial stage of the operation involves inserting the arthroscope into the rear part of the TMJ. This step is relatively straightforward because the proximity of the joint to the ear provides a visible landmark for the surgeon. The anatomical landmarks constituting the ear, eye, and cheekbone aid this approach. Conversely, inserting the working cannula into the front part of the joint is more challenging due to significant anatomical variation among individuals and lack of easy landmarks to rely on. Therefore, facial skin landmarks cannot reliably guide this insertion and the triangulation technique was described as an alternative. This technique involves creating a spatial relationship between three points: the arthroscope, the target area within the joint, and the working cannula's entry point. The term "triangulation" refers to the coordination between the visual axis of the arthroscope and the working cannula's path. The surgeon uses the arthroscope to guide the working cannula to the correct position within the joint. Successful insertion of the working cannula hinges on three conditions: 1) ensuring it avoids damaging nearby vital structures both during and after insertion, 2) positioning it directly within the arthroscope's field of view in the front part of the joint for immediate visibility, and 3) achieving successful insertion on the first attempt, with a maximum allowance for additional 1 or 2 attempts if necessary.

Successful arthroscopy relies on accurately placing the working cannula ideally on the first attempt, and at most on the second or third attempts. Multiple attempts to insert the cannula can lead to puncturing of the joint capsule, causing leakage of the irrigation fluid (saline) and swelling of the face. This edema not only discomforts the patient but also compromises sufficient inflation (hydro-distension) of the joint cavity, thereby complicating the surgical procedure. Scientific literature generally advises halting the procedure after few unsuccessful attempts to insert the working cannula into the correct position.

Furthermore, repeated attempts increase surgical risks, including potential damage to facial nerve branches, blood vessels in the face, and the auditory canal, as well as heightened post-operative pain.

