#### **Reasoning behind conducting the experiment:**

We developed a guide device referred to as Locator-Positioner (LOPO) designed to assist surgeons in accurately and precisely inserting the working cannula into the TMJ. Following the initial insertion of the arthroscope into the joint, which is a relatively straightforward procedure, the LOPO is attached to the outer part of the arthroscope (remaining external to the skin of the face). The LOPO then provides guidance to the surgeon on where and how on the skin to insert the working cannula to precisely align with the end of the arthroscope found within the joint.

Importantly, the LOPO does not enter the patient's body at any point during the operation and should not touch or rest on the skin of the patient's face. It securely attaches to the outer part of the arthroscope, indicating the insertion point and guiding the cannula at the correct angle. Following successful testing on anatomical models, where it demonstrated exceptional accuracy, we aim to evaluate its clinical effectiveness in up to 10 patients to draw conclusive findings.

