### **Goals and Endpoints**

This pilot study aims to recruit up to 10 patients to test the functionality of the LOPO in clinical conditions. The outcome of the study are:

1. The number of attempts required by the surgeon to correctly place the instruments in relation to each other within the joint cavity. No more than three attempts will be made in a single operation.
2. The time elapsed from the insertion of the working cannula until it is clearly visible by the arthroscope (measured in seconds).
3. The number of cases in which the surgeon fails to correctly insert the working cannula, meaning that after three attempts, the cannula is still not properly placed in the joint and not visible by the arthroscope.
4. The improvement of mouth opening after arthroscopy.

Our hypothesis is that the LOPO will shorten the duration of surgery by helping the surgeon insert the working cannula more quickly and easily. It should allow accurate insertion of the working cannula on the first attempt, reducing scuffing of tissues, fluid leakage, swelling, and surgical risks. Using the device does not increase the known risks of surgery.

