#### **Criteria for inclusion, exclusion, and exclusion from the experiment:**

- Inclusion criteria:
  - o Diagnosis of lock-jaw (Closed lock of the TMJ, Wilkes stages 3) based on anamnesis, clinical, and imaging.
  - o Have not undergone surgical intervention in the TMJ in the past.
  - o Adult patients (over the age of 18), not pregnant, and of sound judgment.
- Exclusion criteria:
  - o Patients who are minors, pregnant, or lacking judgment.
  - o Previous surgical intervention of the TMJ.
- Criteria for exclusion from the experiment:
  - o Patients who will not complete post-operative follow-ups as planned.

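### The protocol credits up to ten pilot patients with a conclusive demonstration and states unchanged surgical risk as fact; no failures in ten still leaves a failure rate of up to 31% open

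*Protocol*

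**What the plan says.** Three statements in the protocol describe what the patients are for.

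- The total number of participants and how they will be recruited: "Up to 10 participants are needed to demonstrate that the LOPO device effectively positions the working cannula regardless of anatomical variation among individuals". No other reason is given for the number.
- Reasoning behind conducting the experiment: "we aim to evaluate its clinical effectiveness in up to 10 patients to draw conclusive findings".
- Goals and Endpoints: "This pilot study aims to recruit up to 10 patients to test the functionality of the LOPO in clinical conditions". The Protocol Synopsis and the summary of preclinical knowledge also call the study a pilot.

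Goals and Endpoints lists four outcomes: number of attempts, time to visibility, failures after three attempts, and mouth opening. Method of Analyzing and Processing Results takes up the same four and compares the device patients with patients operated on without the device. It does not give the number of comparison patients.

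On anatomy, the Background explains that placing the working cannula is hard because of "significant anatomical variation among individuals and lack of easy landmarks to rely on".

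On risk, Goals and Endpoints hypothesises that the device should work on the first attempt, "reducing scuffing of tissues, fluid leakage, swelling, and surgical risks". The next sentence is not worded as a hypothesis: "Using the device does not increase the known risks of surgery".

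**The concern.** A pilot that tests functionality and a study that conclusively demonstrates effective positioning whatever the anatomy are different undertakings, and the protocol claims both for the same ten or fewer patients. The stronger claim stands in the sample-size rationale, so it is the stated purpose of the number and not loose background prose. The results are to be published. A clean series of ten could then be presented as proof, although it is a feasibility estimate with a wide margin.

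The risk sentence has the same weakness. It is written as established before any clinical data with the device are reported. The preclinical summary covers anatomical models and reports positioning only. None of the four outcomes is a complication, so the sentence could pass into the report as though the study had supported it.

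**Working it through.** **Inputs.** From the protocol: up to 10 device patients; failure means the cannula is not properly placed and not visible after three attempts; about 70 arthroscopies a year in the department. The protocol gives no confidence level, target rate or precision, so the figure of 10 cannot be reproduced from a formula. Assumed here: 95% confidence, with two-sided and one-sided limits shown; the true failure rates used for illustration; and 70 or 10 comparison patients.

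**1. What a clean series shows.** With no failures in n patients, the exact (Clopper-Pearson) upper limit is 1 − 0.025^(1/n) two-sided and 1 − 0.05^(1/n) one-sided.

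| Failures / n | Two-sided 95% upper limit | One-sided 95% upper limit |
|---|---|---|
| 0/10 | 1 − 0.025^(1/10) = 30.8% | 1 − 0.05^(1/10) = 25.9% |
| 0/8 | 36.9% | 31.2% |
| 0/5 | 52.2% | 45.1% |

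The first row is the best case. One failure in ten gives a two-sided interval of 0.3% to 44.5%. Fewer than ten patients is possible, because the protocol says up to 10 and its halting section can end enrolment.

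**2. How easily a clean series arises.** The probability of no failure in ten is (1 − p)^10. At an assumed true failure rate of 10% this is 0.9^10 = 0.349; at 20% it is 0.8^10 = 0.107.

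**3. Whether the comparison helps, for the failure outcome.** Set 0/10 device failures against the comparison patients with a two-sided Fisher test.

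- With 70 comparison patients (one year's volume, assumed): 23/70 failures gives p = 0.055 and 24/70 gives p = 0.028. At least 24/70 (34%) must fail.
- With 10 comparison patients (assumed): at least 5/10 must fail (p = 0.033).
- With 70 comparison patients and an assumed comparison failure rate of 20%, the chance of 24 or more failures is 0.4%; at 30% it is 25%.

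**4. Whether the comparison helps, for time.** With 10 and 70 patients, a normal approximation at 80% power and two-sided 5% detects (1.96 + 0.84) × √(1/10 + 1/70) = 2.80 × 0.338 = 0.95 standard deviations. Time carries more information than failure, but only a large difference would be found reliably.

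**5. Anatomy.** No anatomical measure appears among the four outcomes or the analysis parameters. The imaging named in the eligibility criteria serves the diagnosis. Ten patients will differ in anatomy, but the results cannot be set against those differences.

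**6. Risk.** The limit in step 1 applies equally to any complication: none in ten is compatible with a true rate of up to 30.8%. That cannot show the absence of an increase, even if every event were counted.

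**The case against.** **Ten is a normal size for a pilot.** This stands. The number is not faulted, only what it is said to prove.

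**Failure after three attempts is the bluntest outcome.** The description of the device gives visibility on the first attempt as its main goal, and effective positioning is not defined as absence of failure. This stands in part. The Fisher figures apply to failures only, and time and attempts may tell more. A reader might infer that the whole comparison is uninformative; step 4 of the working does not support that. Those outcomes still rest on ten device patients or fewer.

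**Anatomy is sampled, since ten people differ.** This stands. A reader might infer that variation is not examined at all, or that the eligibility criteria (Wilkes stage 3, and "Have not undergone surgical intervention in the TMJ in the past") narrow it. The Background speaks of differences between individuals, and nothing in the protocol says that disease stage or surgical history reduces them. The supportable statement is that variation is sampled thinly and not measured.

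**The risk wording is already a hypothesis.** This stands for the reduction in scuffing, leakage, swelling and risk. That expectation also has a measured intermediate, because the Background says "Multiple attempts to insert the cannula can lead to puncturing of the joint capsule, causing leakage of the irrigation fluid" and attempts are counted. It does not cover the sentence that follows. That sentence may be meant as a rationale, since the device stays outside the body, but it is worded as fact.

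**Complications are not ignored.** This stands. The protocol provides for halting on complications and for reporting significant unusual events. A reader might infer that a missing table of complications is a fault; a statistical analysis plan could supply one, so it is not part of this point.

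**Conclusion.** The point holds as a fault of wording in the sample-size rationale, in the reasoning section and in one sentence of Goals and Endpoints. Up to ten patients can give a feasibility estimate. They cannot conclusively demonstrate effective positioning whatever the anatomy, and they cannot establish that risk is unchanged.

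The size is an upper limit of 30.8% on the failure rate in the best case. This rests on ten enrolled patients, no failures and a two-sided 95% level, which is assumed; at one-sided 95% the limit is 25.9%, which leaves the conclusion the same. The result for the comparison depends on an assumed 70 or 10 comparison patients and is limited to the failure outcome. The study can proceed as designed, but its stated claims should be brought into line with what it can show.

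**What to change.** 1. In The total number of participants and in Reasoning behind conducting the experiment, replace the confirmatory wording with: *Up to ten patients allow a feasibility estimate; if no failure is seen in 10, the exact two-sided 95% upper limit for the failure rate is 31% (higher if fewer are enrolled).* Remove the word *conclusive* and the claim that positioning holds whatever the anatomical variation.
2. In Goals and Endpoints, restate the single sentence on known surgical risks as an expectation that this study is not able to test. The hypothesis before it can stay.

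The cost is a more modest stated claim. Patient numbers, outcomes, visits and procedures do not change.

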#### **Criteria for inclusion, exclusion, and exclusion from the experiment:**

- Inclusion criteria:
  - o Diagnosis of lock-jaw (Closed lock of the TMJ, Wilkes stages 3) based on anamnesis, clinical, and imaging.
  - o Have not undergone surgical intervention in the TMJ in the past.
  - o Adult patients (over the age of 18), not pregnant, and of sound judgment.
- Exclusion criteria:
  - o Patients who are minors, pregnant, or lacking judgment.
  - o Previous surgical intervention of the TMJ.
- Criteria for exclusion from the experiment:
  - o Patients who will not complete post-operative follow-ups as planned.

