#### **Summary of existing preclinical knowledge regarding the device:**

The device was tested on anatomical models between August 2017 and February 2018, and it was found to meet the objectives exceptionally well. Multiple doctors in the department,

including interns with no prior arthroscopy experience, conducted several attempts on the models. In all cases, the working cannula was guided by the LOPO device and inserted with great precision to the end of the arthroscope, where it was immediately visible by it. The experiments were conducted in the operating room at Sheba Medical Center using the same set of standard arthroscopic tools.

In this pilot experiment, we will use the same standard set of arthroscopic tools that is regularly used at Sheba Medical Center. It is important to note that the LOPO has been designed according to the dimensions of the arthroscopic tool set available at Sheba.

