#### **Details of the research program and clinical follow-up:**

- Patients that are referred for TMJ arthroscopy at our department will be asked if they agree to participate in the LOPO experiment. Patients will receive standard treatment in terms of hospitalization and examinations.
- Follow-up reviews will take place in our clinic.
- The initial follow-up period is six months.
- Patients may be invited for further follow-up visits as a routine practice in our department.

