**Participant Privacy and Confidentiality of Collected Information:**

- Patients diagnosed with lock-jaw who need TMJ arthroscopy will be offered the option to use the LOPO device during their surgery. They will receive an informational letter explaining the procedure and the use of the device.
- Interested patients should consult with their family doctor, presenting the explanatory letter for further advice. Regardless of their decision to participate in the trial, all patients will receive standard care in our department, including admission, hospitalization, discharge, and periodic follow-ups after surgery.
- A database containing the names of the patients (up to 10) and the experiment results (studied indices) will be maintained in an Excel sheet on a secure computer within the department.

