**Conditions for Halting the Medical Experiment:**

- If the LOPO device does not perform as expected, based on its performance with anatomical models, its use will be halted immediately, and no further patients will be enrolled in the experiment.
- The use of the LOPO will also be immediately discontinued in the event of any known or unforeseen complications arising from the operation

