**Method of Analyzing and Processing Results:**

- The data from the ten patients using the device will be compared with data from patients undergoing TMJ arthroscopy without using the LOPO device. The following parameters will be evaluated:
  - o Time elapsed from insertion of the working cannula until it is clearly visible through the arthroscope.
  - o Number of attempts made by the surgeon to correctly position the instruments within the joint cavity (limited to three attempts per surgery, following standard practice).
  - o Number of cases where the surgeon failed to correctly insert the working cannula, despite three attempts, as observed through the arthroscope.

- Measurements of maximal mouth opening of the patients undergoing the procedure, before as compared to after arthroscopy.

Contact:

[name]

Telepohone: [name]

Email: [[contact]](mailto:[contact]), [[contact]](mailto:[contact])

[name]

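### The follow-up exclusion rule can remove an operated patient, including a failed insertion, from outcomes that are already complete when surgery ends

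*Protocol*

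**What the plan says.** The eligibility section of the protocol has three lists: inclusion criteria, exclusion criteria, and a third headed "Criteria for exclusion from the experiment". The third list has a single item: "Patients who will not complete post-operative follow-ups as planned". *Details of the research program and clinical follow-up* adds: "The initial follow-up period is six months".

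*Goals and Endpoints* lists four outcomes: the number of attempts (at most three), the seconds until the cannula is visible, "The number of cases in which the surgeon fails to correctly insert the working cannula", and the improvement in mouth opening.

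Two other places bear on who is counted. *Method of Analyzing and Processing Results* says: "The data from the ten patients using the device will be compared with data from patients undergoing TMJ arthroscopy" performed without the device. The privacy section says: "A database containing the names of the patients (up to 10) and the experiment results (studied indices) will be maintained". Neither mentions patients who fall under the third list.

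**The concern.** The rule turns on an event after surgery, but three of the four outcomes are settled during surgery. A patient who misses a later visit has complete data on attempts, time and success or failure of insertion. Excluding that patient from the experiment discards valid operative data for a reason that has nothing to do with those outcomes, and does so after the insertion result is known.

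Insertion is the core of this pilot: the protocol justifies its sample by the need to show that the device positions the cannula. Outcome 3 is a count of failures in at most 10 patients, so losing one failed case can turn a report of one failure into a report of none. The comparison could also become uneven, because no follow-up exclusion is stated for the patients operated on without LOPO.

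**Working it through.** The protocol gives no failure rate, loss rate or precision target, so there is no stated figure to reproduce. The check has two parts: when each item becomes known, and what one exclusion does to the reported result.

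**Timing**

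| Item | When known |
|---|---|
| Outcome 1, attempts | End of surgery |
| Outcome 2, seconds to visibility | End of surgery |
| Outcome 3, failure after three attempts | End of surgery |
| Outcome 4, mouth opening before and after | Can need a follow-up visit |
| Completion of follow-up | After surgery, up to six months later |

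Only outcome 4 can be made unavailable by a missed visit. The rule is not limited to outcome 4; its heading refers to the experiment as a whole.

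**Effect of one exclusion (illustration, post-surgery reading)**

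Inputs: n = 10, the protocol's maximum, and one failed insertion (assumed). Intervals are exact (Clopper-Pearson) 95%. For zero failures in n the upper limit is 1 − 0.025^(1/n).

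- All operated patients kept: 1/10 = 10% (0.3% to 44.5%).
- Failed case excluded: 0/9 = 0%, upper limit 1 − 0.025^(1/9) = 33.6%.
- A successful case excluded instead: 1/9 = 11.1% (0.3% to 48.2%).

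Mean attempts, taking nine first-attempt successes and counting the failure as three attempts:

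- All kept: (9 × 1 + 3)/10 = 1.2.
- Failed case excluded: 9/9 = 1.0.
- One success excluded: (8 × 1 + 3)/9 = 1.22.

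**If a failure stops the study**

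Under the halting conditions, if the device does not perform as it did on the models, "its use will be halted immediately, and no further patients will be enrolled in the experiment". The preclinical summary reports: "In all cases, the working cannula was guided by the LOPO device and inserted with great precision to the end of the arthroscope". If a failed insertion triggers this rule, at most one failure accrues. A failure in patient k then gives 1/k, and excluding that patient gives 0/(k − 1):

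| k | Kept | Failed case excluded |
|---|---|---|
| 3 | 1/3 = 33.3% (0.8% to 90.6%) | 0/2, upper limit 84.2% |
| 5 | 1/5 = 20% (0.5% to 71.6%) | 0/4, upper limit 60.2% |
| 10 | 1/10 = 10% (0.3% to 44.5%) | 0/9, upper limit 33.6% |

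On the pre-surgery reading none of these changes occurs.

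**The case against.** The strongest reply is that the rule governs participation and not analysis. The protocol does not say that data already collected are deleted. Its analysis section defines the group by use of the device, and its database covers up to 10 patients with their results. Both lean towards keeping the data, and the choice of analysis set could be left to an SAP that is not shown. This has some weight. But neither place says that a patient excluded under the third list stays in the results, and a reference to ten patients could also mean ten who remain after replacement. The point is also not that an analysis set is missing: the protocol states an exclusion, and its wording is broader than the outcomes that it can sensibly affect.

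Second, the future tense may describe expected attendance judged before surgery. That reading is possible. Against it, the item stands outside the entry exclusions, where a screening criterion would belong.

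Third, the count changes from one to none only if the same patient both fails insertion and misses follow-up. With independent failure rate f and loss rate d, the chance of at least one such patient among 10 is 1 − (1 − f × d)^10. That is 2.5% for f = d = 5%, 9.6% for f = d = 10%, and 18% for f = 10% and d = 20%. All these rates are assumed, as the protocol gives none. If loss is unrelated to the insertion result, the expected failure proportion does not change. This stands, and it limits the size of the problem. Valid operative data would still be lost from a very small sample.

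Fourth, a halt after a failure would make that failure evident. That is fair, but the halting conditions do not say that the case is counted in outcome 3.

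**Conclusion.** The concern holds, with moderate confidence, and should be fixed. As worded, the rule can remove an operated patient from three outcomes that do not depend on follow-up, and nothing in the protocol prevents it. The size is one case in at most 10: a reported failure count of one can become zero, or mean attempts can move from 1.2 to 1.0. The intervals are wide and overlap, so what is at risk is the reported count and not a precise rate. The conclusion rests on the post-surgery reading, which the separate list favours but does not prove; on the pre-surgery reading there is no effect. The protocol shows no differential loss, so no bias in a given direction is claimed.

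**What to change.** State that the follow-up criterion, if kept, applies only before surgery. Then add wording to this effect: *Every patient in whom LOPO-guided insertion is attempted is included in outcomes 1 to 3, whatever their follow-up. A patient without the follow-up mouth-opening measurement is missing for outcome 4 only, and the number of such patients and the reasons are reported.* Count the patients operated on without LOPO on the same basis, so that the two groups match.

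The cost is one or two sentences in the protocol, plus the line on the comparison group. No extra patients, visits or procedures are needed. Compared with applying the exclusion, the reported failure rate may move slightly in either direction. If the pre-surgery reading was intended all along, the change does no harm.
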